### **Study Timelines**

For participants, this study is expected to take 7.5 months to complete. Based on our experiences with a recent SGB pilot study, we anticipate the screening, intake, and treatment scheduling process to take approximately 1 month to complete. The treatment process is expected to take two weeks to complete. The remaining six month duration of the study will be spent completing follow-ups, which will occur up to six months following participants' second SGB/placebo saline injection.

### **Inclusion and Exclusion Criteria**

Individuals are *eligible* for the current study if they:

1. Are 18 years or older
2. Are fluent in English
3. Have experienced a Criterion A traumatic event during their lifetime
4. Have a PTSD diagnosis verified via the Clinician Administered PTSD Scale for DSM-5
5. Have not previously received an SGB
6. Have a smartphone that they can use for the entire duration of the study
7. Are willing and able to receive 2 injections (SGB or placebo) 2 weeks apart at the Rush Pain Clinic
8. Are willing and able to participate in daily CPT or Daily Monitoring over the course of one week
9. Are willing and able to complete self-report measures and clinician-rated assessments at multiple time points over the course of the study

Individuals are *excluded* from the current study if:

1. The traumatic event occurred in the past month

2. They are currently suicidal or homicidal (i.e., plan and intent)
3. They have unmanaged psychosis or mania
4. They have not been on a stable dose of psychotropic medication for at least one month by the time of the baseline assessment or are planning to change their medications within 3 months of starting their participation in the study
5. They have completed an evidence-based cognitive behavioral PTSD treatment (e.g., CPT or Prolonged Exposure) in the past 3 months or are currently receiving an evidence-based PTSD treatment
6. They have an intellectual disability or significant cognitive impairment that would prevent them from engaging fully in treatment
7. They are currently on any blood-thinning medications or have a coagulopathy
8. They have any of the following conditions: a recent myocardial infarction, glaucoma, a pre-existing contralateral nerve palsy, severe emphysema, or a cardiac conduction blockade.
9. They are allergic to any of the medications injected (i.e., ropivacaine, lidocaine, propofol)
10. They have an active infection
11. They have a serious or unstable medical illness or instability for which hospitalization may be likely within the next year
12. They have a visual or auditory impairment that would prevent them from fully participating in study activities
13. They are involved with current legal actions related to the traumatic event that is anticipated to be targeted during treatment
14. They have substance dependence that, in the judgment of the Principal Investigator, may require hospitalization if substances were discontinued.
15. Subjects who, at the time of consent, appear to have extenuating life circumstances (e.g., unstable housing, no internet access, etc.) which, in the judgment of the Principal Investigator, could affect the ability to deliver the intervention with fidelity

These inclusion criteria are as broad as possible to allow for the trial to apply to real-world clinical settings. The exclusion criteria were chosen to identify individuals that have certain comorbidities or circumstances that would make engagement in a cognitive-based treatment difficult or potentially interfere with a clinician's ability to deliver the intervention with fidelity. The exclusion criteria chosen would be considered as a part of standard clinical care outside of a research setting for those seeking CPT or SGB treatment for PTSD.

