### ***Virtual Baseline Assessments***

Under the supervision of the Principal Investigator, who is a licensed clinical psychologist, trained study staff, with at least a Bachelor's degree and who are not providing the treatment, will conduct structured diagnostic interviews. These interviews are to determine eligibility by confirming a diagnosis of PTSD, as assessed by a gold-standard Clinician Administered PTSD Scale for DSM-5. Completion of the baseline assessment will take approximately 4 hours and may take place over 1-2 days, depending on the participant's availability. The baseline assessment will be conducted virtually via the HIPAA-compliant telehealth platform Microsoft Teams. All baseline assessments will be audio/video recorded for research purposes and to ensure that assessments were delivered with fidelity.

Study staff will also securely email the full self-report assessment battery to intake participants via REDCap, which takes approximately 40 minutes to complete. Individuals who meet exclusion criteria during the virtual baseline visit or who choose not to participate will be referred for other treatment/resources as indicated.

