### ***Management of Risk***

The risk for serious complications associated with a SGB procedure will be managed through the use of ultrasound guidance. When placed using ultrasound guidance, SGB has been shown to have a high safety profile. Subjects will be asked to refrain from eating from midnight the night before the procedure and only be allowed sips of water the morning of the procedure. Subjects will be instructed not to drive or operate heavy machinery for 24 hours after the

procedure. Subjects will be instructed not to eat food or drink for four hours after the procedure or until their ability to swallow as normal has returned. If the study physician deems the risks associated with the SGB treatment to be too severe for the participant, the study physician may, in correspondence with the PI, remove the participant from the study.

Participants may experience distress during CPT treatment or Daily Monitoring. Participants' suicidality will be assessed by the treating clinicians on an ongoing basis and assessed formally at the baseline as well as each follow-up time point using the Columbia Suicide Severity Rating Scale (C-SSRS). If a participant indicates having "Thoughts that [they] would be better off dead or of hurting [themselves] in some way" more than half the days (2) or nearly every day (3), the study clinician will conduct a safety assessment. If any participant becomes actively suicidal with intent, the study clinician will refer the participant to a higher level of care (i.e., psychiatric, medical, or emergency services).

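### Exclusion 2 bars suicidality only with both plan and intent, while the referral rule acts on intent and mentions no plan, so no stated suicidality criterion bars intent without a plan (minor)

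*Protocol*

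**What the plan says.** **Entry.** Under Inclusion and Exclusion Criteria, exclusion 2 is "They are currently suicidal or homicidal (i.e., plan and intent". None of the other 14 exclusions and none of the nine inclusion criteria names suicidality. At the baseline visit the stated rule is "Individuals who meet exclusion criteria during the virtual baseline visit or who choose not to participate will be referred for other treatment/resources as indicated". Random Assignment of Treatments then randomises those who are eligible, and the first injection comes before CPT session one.

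**On study.** Management of Risk says "If any participant becomes actively suicidal with intent, the study clinician will refer the participant to a higher level of care", and lists psychiatric, medical or emergency services as examples. The same section says that "suicidality will be assessed by the treating clinicians on an ongoing basis" and that it is "assessed formally at the baseline as well as each follow-up time point using the Columbia Suicide Severity Rating Scale (C-SSRS"). It also stops CPT or Daily Monitoring for anyone *actively suicidal*, a term it does not define. Such a person may enrol later once stable, subject to the eligibility requirements.

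**The concern.** In exclusion 2, *i.e.* defines what counts as suicidal, and *and* joins two conditions that must both hold. The referral rule names only intent. Read together, the protocol treats intent as serious enough for psychiatric or emergency referral, yet does not list it as a reason against entry unless a plan is also present.

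What is at stake is a participant-safety and eligibility question. Someone whom the protocol's own rule would send to a higher level of care is not made ineligible for randomisation and an invasive neck injection. The gap is avoidable, because the instrument that would show intent is already given at baseline, before randomisation.

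**Working it through.** No figure in the protocol needs reproducing. The check sets the two rules side by side over the possible combinations of plan (yes/no) and intent (yes/no), 2 × 2 = 4.

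| Plan | Intent | Barred by exclusion 2 as worded | At the referral trigger |
|---|---|---|---|
| yes | yes | yes | yes |
| no | yes | **no** | **yes** |
| yes | no | no | no |
| no | no | no | no |

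- Barred at entry: 1 combination.
- At referral level: 2 combinations. The second rests on an inference: the referral rule is silent about a plan, and I read that silence as not requiring one.
- At referral level but not barred: 2 − 1 = 1, intent without a plan.
- With exclusion 2 based on intent: barred 2, referred 2, so 2 − 2 = 0 remain.

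The two rows without intent are not part of the point. The table counts categories and says nothing about how often each occurs.

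**Could another criterion bar the intent-only person?** Three come near, none by naming suicidality:

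- Inclusion 8: "Are willing and able to participate in daily CPT or Daily Monitoring over the course of one week". This depends on a judgement of *able*.
- Exclusion 11: "They have a serious or unstable medical illness or instability for which hospitalization may be likely within the next year". This could be stretched to psychiatric instability, but the wording leans medical.
- Exclusion 15 concerns life circumstances which, "in the judgment of the Principal Investigator, could affect the ability to deliver the intervention with fidelity". Its examples are housing and internet access.

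**Room for extra screen failures.** Target Population and Sample Size plans 270 recruits for 180 who start treatment: 270 − 180 = 90, and 90/270 = 33.3%. This lies inside the 25–50% loss that the section anticipates.

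**The case against.** The strongest reply is that the protocol already protects this person.

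- **Referral is mandatory and plausibly reaches baseline.** Consent comes before the baseline assessment, so a person with intent on the baseline C-SSRS is already a consented participant. The protocol also provides for a crisis during a virtual assessment, and the baseline visit is virtual. This largely stands: such a person would probably be referred. It does not close the gap, because the rule speaks of someone who *becomes* suicidal and nowhere says that a referred person is not randomised. Referral is not ineligibility.
- **Inclusion 8 read with the therapy stop.** Someone who could not be kept in the therapy week is hard to call able to take part in it. This is a fair reading and may work in practice. It depends on an undefined term and on someone making the connection.
- **Loose wording.** *Plan and intent* may be shorthand for active as opposed to passive ideation, and the re-enrolment sentence suggests that the authors saw active suicidality as incompatible with eligibility. If so, the text misstates what was meant, and the same edit corrects it.
- **A response rule may sensibly start below an exclusion threshold, and entry is meant to be broad.** Both are true in general. Here, though, the response is referral to a higher level of care. The milder step, a safety assessment, has its own separate trigger in the same section.

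A reader might infer that the protocol leaves suicidal entrants without safeguards, or that the therapy stop flatly contradicts exclusion 2. The documents support neither. The safeguards above exist, and because *actively suicidal* is undefined and re-enrolment refers back to eligibility, the stop can be read consistently with exclusion 2.

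**Conclusion.** The point holds as a minor mismatch between the entry threshold and the on-study safety threshold. One of the four plan-by-intent combinations, intent without a plan, meets the referral trigger but no stated suicidality exclusion. Whether such a person stays out rests on the referral rule being treated as a bar to randomisation, on inclusion 8, or on investigator judgement.

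This assumes that *and* in exclusion 2 is meant literally and that the referral rule's silence on a plan means none is required. The number of people affected is unknown and none is assumed. There is no effect on power or alpha, and nothing in the documents suggests that the criterion would be applied differently by arm. Severity: minor, an optional improvement.

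**What to change.** 1. Reword the suicidality part of exclusion 2 to *current active suicidality with intent, with or without a plan*, judged on the baseline C-SSRS. Leave the homicidal part as it is, since the referral rule does not address it.
2. In the therapy-stop paragraph of Management of Risk, state that *actively suicidal* includes at least intent, with or without a plan, as judged by the clinician at the time, and that re-enrolment requires the revised exclusion 2 not to be met. This sets a minimum and should not narrow the stop.
3. Leave the referral rule unchanged.

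**Cost.** Wording in two places. No new instrument or visit is needed: the Assessment Grid already has the C-SSRS at baseline. It schedules none in the therapy week, when the ongoing clinician assessment applies. There may be a few more screen failures, to be absorbed within the 90 already allowed for, and entry becomes slightly narrower than the stated aim of broad criteria.

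**Limit.** The change tests intent at baseline only. Screening, intake and scheduling take about a month, so intent that arises between baseline and the first injection would still be handled by the on-study rules.

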## **Study Activities**

### ***Eligibility Phone Screening***

Individuals who are interested in participating in the proposed study will call study staff in response to study recruitment flyers or will be called by the study staff once they have been referred. The eligibility screening will be conducted over the phone. Interested individuals will be asked for their verbal consent to participate in the eligibility screening and then screened to determine potential eligibility. Individuals who meet exclusion criteria during the screening or

virtual baseline visit or who choose not to participate will be referred for other treatment/resources as indicated. Potentially eligible individuals will be sent the electronic consent form.

### ***Informed Consent***

Informed consent will be obtained by trained members of the study staff before the baseline assessment. Potential participants will be emailed the electronic consent form via REDCap, a HIPAA-secure platform. Study staff will call and explain the study to the potential participants and answer any questions they have. Potential participants will be encouraged to carefully read the entire consent form and to take their time to consider if they would like to participate. Potential participants can take as much time as they need to decide if they would like to participate and reach out to study staff with any questions they may have. Potential participants will be allowed to discuss the study with others (e.g., an outside treatment provider) if they would like to before consenting.

If at any time reconsent is needed, participants will be sent a new electronic consent form via REDCap and study staff will inform them of any changes that were made.

### ***Virtual Baseline Assessments***

Under the supervision of the Principal Investigator, who is a licensed clinical psychologist, trained study staff, with at least a Bachelor's degree and who are not providing the treatment, will conduct structured diagnostic interviews. These interviews are to determine eligibility by confirming a diagnosis of PTSD, as assessed by a gold-standard Clinician Administered PTSD Scale for DSM-5. Completion of the baseline assessment will take approximately 4 hours and may take place over 1-2 days, depending on the participant's availability. The baseline assessment will be conducted virtually via the HIPAA-compliant telehealth platform Microsoft Teams. All baseline assessments will be audio/video recorded for research purposes and to ensure that assessments were delivered with fidelity.

Study staff will also securely email the full self-report assessment battery to intake participants via REDCap, which takes approximately 40 minutes to complete. Individuals who meet exclusion criteria during the virtual baseline visit or who choose not to participate will be referred for other treatment/resources as indicated.

### ***Setting Up Wearable Device***

If eligible for the study following baseline assessments, participants will be mailed a wearable sensor device called a Fitbit to wear on their wrists to measure metrics commonly collected by Fitbit devices (e.g., heart rate variability, heart rate, steps, calories). Participants will be asked to wear the Fitbit between baseline and the six-month follow-up. Following the six-month follow-up, participants will be asked to return the Fitbit device through the mail. Study staff will provide pre-paid shipping labels and shipping instructions at no cost to participants. Participants will not be charged for damaging or failing to return their assigned devices.

### ***Random Assignment of Treatments***

Random assignment of eligible participants will occur in two steps using a custom computer randomization algorithm. First, participants will be randomly assigned to receive either two active SGB injections or two placebo saline injections. In the second stage of random assignment, participants will be randomly assigned to receive 1-week of CPT or daily symptom monitoring.

As there will only be three treatment conditions of this study (SGB+CPT, SGB+Daily Monitoring, and Placebo Injection+CPT), individuals that are randomly assigned to the placebo injection group in the first stage of random assignment will automatically be assigned to receive CPT.

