## **Scientific Review**

### ***First-Line PTSD Treatments***

PTSD is a debilitating mental health condition that impacts approximately 23% of Veterans. Between 2001-2017, the average incidence rate of PTSD in the U.S. military was 7.88 per 1000 service members, with a peak incident rate of 12.94. Moreover, PTSD is associated with high rates of comorbidity and high degrees of functional impairment, more so than any other mental health disorder. Untreated PTSD has been shown to lead to substantial impairments in work, home, and social functioning, increased risk of suicide, and poorer long-term physical health outcomes.

The Veterans Administration and Department of Defense (VA/DoD) Clinical Practice Guidelines recommend CPT, among other interventions, as a first-line psychotherapeutic intervention for the treatment of PTSD. CPT can produce large PTSD symptom reductions. These PTSD symptom reductions are lasting and can be maintained for 10 years or more. CPT has been successfully used with a wide range of populations, including service members and Veterans. The primary mechanism of action in CPT is hypothesized to be a reduction in negative trauma-related cognition about oneself, others, and the world.

While CPT is traditionally delivered weekly over 12 sessions, our research group and others have recently demonstrated that CPT can be successfully administered in as little as a single week. In our recently completed clinical trial we also demonstrated that 1-week massed CPT can be effectively delivered via telehealth. Completion rates for 1-week massed CPT were extremely high with 96% of participants completing the entire course of treatment, suggesting excellent feasibility. The results from the 1-week massed CPT trial suggest that 87% of study participants experienced clinically significant PTSD severity changes after the single week, with

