## **Research Plan**

### **Objectives**

To systematically address questions surrounding improving PTSD treatment, the proposed 3-arm randomized controlled clinical trial will directly compare the combination of CPT+SGB vs. CPT (+Placebo) vs. SGB (+daily monitoring) in a total of 180 service members, Veterans, and civilians with PTSD. Short- and longer-term (up to 6-month follow-up) impacts of the respective interventions on both PTSD symptoms and functioning will also be assessed.

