#### ***Objective 1***

Determine the efficacy of combining CPT and SGB for reducing PTSD symptoms and improving functioning. H1a: Participants who receive CPT+SGB will experience greater reductions in PTSD symptoms based on clinician-administered and self-reported PTSD assessments and greater improvements in functioning compared to each intervention alone. H1b: Clinician-administered and self-reported PTSD symptoms will reduce to a greater extent immediately after and 3- and 6-months following treatment for participants assigned to the CPT+SGB condition vs. those who receive CPT (+Placebo) and SGB (+daily monitoring).

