#### ***Objective 2***

Probe changes in negative posttrauma cognitions and sympathetic/parasympathetic balance as potential complementary treatment mechanisms. H2a: Negative posttrauma cognitions will improve over the course of CPT+SGB and CPT and improve to a greater extent than for individuals who receive SGB. H2b: Greater reduction in the sympathetic/parasympathetic balance, assessed via heart rate variability (HRV), will be experienced by individuals assigned to the CPT+SGB and SGB conditions compared to individuals who receive CPT. H2c: Changed in negative posttrauma

cognitions and sympathetic/parasympathetic balance will predict short- and longer-term (6-month) PTSD symptom reductions and functional improvement.

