### **Target Population and Sample Size**

We will consent and enroll a total of approximately 180 service members, veterans, and civilians with PTSD. Based on our prior trials with this population, we anticipate that ~25-50% of potential participants will not meet inclusion criteria or will not start treatment. Thus, we plan to recruit 270 individuals to have a final sample of 180 service members, veterans, and civilians who start treatment. We will purposely oversample for veterans and service members with the goal of recruiting approximately  $n = 90$  veterans and/or service members and approximately  $n = 90$  civilians for the final sample.

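### Does the two-step randomisation, which sends every placebo participant to CPT, leave the three arms unbalanced?

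*Protocol*

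**What the plan says.** Under Random Assignment of Treatments, the Protocol uses a custom computer algorithm in two steps. The first is "First, participants will be randomly assigned to receive either two active SGB injections or two placebo saline injections". The second is "In the second stage of random assignment, participants will be randomly assigned to receive 1-week of CPT or daily symptom monitoring". Because only three conditions exist, "individuals that are randomly assigned to the placebo injection group in the first stage of random assignment will automatically be assigned to receive CPT".

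No probability or ratio is attached to either step. Objectives gives the total: the trial "will directly compare the combination of CPT+SGB vs. CPT (+Placebo) vs. SGB (+daily monitoring) in a total of 180 service members", together with Veterans and civilians. Target Population and Sample Size repeats that total: "we plan to recruit 270 individuals to have a final sample of 180 service members, veterans, and civilians who start treatment". The figures of about 90 and about 90 in that section divide veterans and service members from civilians. They are not arm sizes.

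The hypotheses use the arms in different ways. H1a (Objective 1) expects CPT+SGB to give greater PTSD symptom reductions and "greater improvements in functioning compared to each intervention alone", so it involves two contrasts that share the CPT+SGB arm. H2a (Objective 2) sets the two CPT arms against SGB. H2b expects an effect on sympathetic/parasympathetic balance that "will be experienced by individuals assigned to the CPT+SGB and SGB conditions compared to individuals who receive CPT".

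**The concern.** Two either/or draws with one branch closed do not give three equal arms by default. A programmer who codes each draw as a fair coin puts half the sample on placebo with CPT and a quarter in each SGB arm. The combination arm, which is the treatment under test and enters both H1a contrasts, would then be one of the two smallest. The Protocol does not mention the deliberate 2:1 first step that equal arms would need.

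At stake is precision on CPT+SGB versus SGB+Monitoring. Allocation takes effect at enrolment, so no later analysis can recover what an inefficient split loses. With even draws, 60 in each SGB arm would need 240 participants, not 180.

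**Working it through.** **Inputs.** From the Protocol: N = 180, three arms, all placebo participants routed to CPT, two H1a contrasts. Assumed, because the Protocol states none of them: the ratio at each step, a common SD, two-sided alpha of 0.05, the effect sizes, complete outcome data, and unadjusted two-sample t-tests. The Protocol shows no power calculation or arm sizes, so it has no figure of its own to reproduce.

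**Arm sizes.** Expected size = N × P(step 1) × P(step 2).
- Both steps even: 180 × 1/2 = 90 CPT+Placebo; 180 × 1/2 × 1/2 = 45 in each SGB arm.
- First step 2:1 SGB to placebo, second step even: 180 × 1/3 = 60 CPT+Placebo; 180 × 2/3 × 1/2 = 60 in each SGB arm.
- First step 3:2, second step even: 72 CPT+Placebo and 54 in each SGB arm.

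All three fit the wording.

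**Variance of a difference in means (SD = 1): 1/n₁ + 1/n₂.**

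| Contrast | 60/60/60 | 90/45/45 | Ratio |
|---|---|---|---|
| CPT+SGB vs SGB+Monitoring | 1/60 + 1/60 = 0.0333 | 1/45 + 1/45 = 0.0444 | 1.33 |
| CPT+SGB vs CPT+Placebo | 1/60 + 1/60 = 0.0333 | 1/45 + 1/90 = 0.0333 | 1.00 |
| H2a, CPT arms pooled vs SGB+Monitoring | 1/120 + 1/60 = 0.0250 | 1/135 + 1/45 = 0.0296 | 1.19 |
| H2b, SGB arms pooled vs CPT+Placebo | 1/120 + 1/60 = 0.0250 | 1/90 + 1/90 = 0.0222 | 0.89 |

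Pooling for H2a and H2b is one reading of Objective 2; the Protocol does not prescribe it.

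**Power for CPT+SGB vs SGB+Monitoring (noncentral t).**

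| Assumed difference | 60 vs 60 | 45 vs 45 |
|---|---|---|
| 0.4 SD | 58% | 47% |
| 0.5 SD | 78% | 65% |
| 0.6 SD | 90% | 80% |
| 0.7 SD | 97% | 91% |
| 0.8 SD | 99% | 96% |

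The difference detectable with 80% power moves from 0.52 to 0.60 SD. With 54 per SGB arm, power at 0.5 SD is 73%. CPT+SGB vs CPT+Placebo has 78% power at 0.5 SD under either split.

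**Chance that both H1a contrasts succeed (simulated t-tests), 60/60/60 against 90/45/45.**
- 0.5 SD on both: 65% against 58%.
- 0.5 SD over CPT+Placebo and 0.7 SD over SGB+Monitoring: 76% against 74%.
- 0.5 SD and 0.8 SD: about 77% against 77%.

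**Pooled contrasts at 0.5 SD.** H2a 88% against 82%; H2b 88% against 92%.

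**The case for a change.** The strongest case for a change is that the allocation ratio belongs in a protocol, and that this is the section where it would stand. The scheme as worded allows a split that costs precision on one H1a contrast and improves neither. Stating the ratios would take one sentence and no extra participants. The arithmetic behind this is sound. It is also true that the Protocol does not document how much CPT adds over SGB, so a moderate effect, where the loss is largest, cannot be excluded.

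What stands is that the ratio is unstated and that, if both draws were in fact even, one contrast would lose precision. The step from there to a design fault does not stand. The 90/45/45 split appears nowhere in the Protocol and is not implied by it. The authors explain the routing by the existence of only three conditions, so they knew the tree was asymmetric, and they describe the algorithm as custom-built. A total of 180 also divides evenly into 60 per arm.

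Nor is equal allocation uniquely best for Objective 1. Because CPT+SGB is shared, about 74 in that arm and 53 in each comparator gives 1/74 + 1/53 = 0.0324 on both contrasts, about 3% below 0.0333. Under 90/45/45, pooled H2b would gain. The powers above are also on the low side if the analysis adjusts for baseline: with an assumed baseline correlation of 0.6, a raw difference of 0.5 SD gives 92% at 60 per arm and 83% at 45.

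**Conclusion.** No change to the plan follows. The Protocol leaves out the ratio at each randomisation step and the target arm sizes. This is a gap that the trial team can close by reading the settings of its own algorithm. If the first step is weighted 2:1, the arms are 60/60/60 and nothing is lost.

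If both steps are even, randomisation still protects every comparison and estimates stay unbiased. The cost is 33% more variance on CPT+SGB versus SGB+Monitoring, none on CPT+SGB versus CPT+Placebo, some on a pooled H2a, and a gain on a pooled H2b. The affected contrast is the one where a large effect is most plausible: the Protocol states that "CPT can produce large PTSD symptom reductions" and uses daily monitoring as a psychotherapy placebo. There, power goes from 97% to 91% at 0.7 SD and from 99% to 96% at 0.8 SD, and joint H1a success hardly moves. At 0.5 SD on both contrasts the joint loss is about 8 points (65% to 58%, or 65.3% to 57.6% unrounded).

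All these figures are conditional on even draws, assumed effect sizes, complete data and unadjusted tests. They illustrate what an unconfirmed setting could cost. They do not show that the plan as written gives a wrong result.
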